8.2.1.9 TREATMENT OF OVERDOSE

For this study, any dose of ANB019 or placebo administered in a volume exceeding the planned dosing detailed in [Table 2](#) (Dose Strength[s]/Dosage Level[s]) will be considered an overdose. For ANB019, this means a dose greater than 400 mg received within a 24-hour time period on Day 1 and Day 113 (for subjects assigned to placebo during the placebo-controlled period) and greater than 200 mg on Days 29, 57, 85, 113 (for subjects assigned to ANB019 during the placebo-controlled period), 141, 169, and 197.

In the improbable event of a suspected overdose, the following procedures should be executed:

- Administration is to be discontinued.
- The subject is to be monitored clinically.
- Supportive measures are to be undertaken as clinically indicated.
- Electrocardiography and clinical laboratory evaluations (ie, blood glucose, hepatic enzymes, creatinine, blood urea nitrogen, creatine kinase (CK), and complete blood count) are to be performed and followed until all values return to Baseline levels and AEs subside, if applicable.

No information on overdose, maximum tolerated dose, or dose-limiting toxicities for ANB019 has been established at this time and since there are no known antidotes for ANB019, the treatment of overdose is at Investigator's discretion.

DocuSign Envelope ID: E4BE9C16-DB1E-4354-B874-2109B7254DAA

Efficacy and Safety of ANB019 in Subjects with Ichthyosis
Protocol ANB019-206

Version 1.0
30 October 2020

In the event of an overdose, the Investigator should:

1. Contact the Medical Monitor immediately.
2. Closely monitor the subject for any AE/SAE and laboratory abnormalities and follow-up until resolution.
3. Obtain a serum sample for PK analysis soon after the dose for SC administration.
4. Document the quantity of the excess dose as well as the duration of the overdose in the eCRF.

Decisions regarding dose interruptions will be made by the Investigator in consultation with the Medical Monitor based on the clinical evaluation of the subject.

8.2.2 HEIGHT AND WEIGHT

Height (cm) and weight (kg) will be collected to calculate the BMI. Height and weight will be measured at the time points specified in the SoA (see [Section 1.3](#)).

8.2.3 CHEST X-RAY

Bidirectional posterior-anterior and lateral view chest X-ray, or as indicated by local treatment guidelines or practice, will be performed at screening (see Section 1.3). If a chest X-ray was performed within 6 months of screening and no clinically significant abnormality was observed, it can be skipped at screening.

8.2.4 PHYSICAL EXAMINATIONS

Complete physical examinations will be performed at the time points indicated in the SoA (see Section 1.3).

A complete physical examination will include assessments of general appearance; skin; head/neck; pulmonary, cardiovascular, gastrointestinal, lymphatic, and musculoskeletal system; extremities; eyes; nose; throat; and neurologic status.

A detailed examination of the skin should be performed at the time points indicated in the SoA for the efficacy assessments (eg, IASI).

Investigators should pay special attention to clinical signs related to previous serious illnesses.

8.2.5 VITAL SIGNS

Body temperature (°C), pulse rate (bpm), blood pressure (mmHg), and respiratory rate (breath/min) will be assessed at the time points specified in SoA (see Section 1.3).

Blood pressure and pulse rate will be assessed in a seated position with a completely automated device. Manual techniques will be used only if an automated device is not available.

Blood pressure and pulse rate measurements should be preceded by at least 5 minutes of rest for the subject in a quiet setting without distractions (eg, television, cell phones).

Vital signs including body temperature, respiratory rate, and pulse rate (after at least 5 minutes rest) should be measured once. Arterial blood pressure should be measured twice (at intervals of at least 5 minutes), using a validated device.

DocuSign Envelope ID: E4BE9C16-DB1E-4354-B874-2109B7254DAA

Efficacy and Safety of ANB019 in Subjects with Ichthyosis
Protocol ANB019-206

Version 1.0
30 October 2020

8.2.6 ELECTROCARDIOGRAMS

A single 12-lead ECG will be obtained at the time points specified in the SoA (see [Section 1.3](#)) using a validated ECG machine that automatically calculates the heart rate and measures RR, PR, QRS, QT, and QTcF intervals.

Additional information will be provided in a separate manual.

The ECG will be reviewed by the Investigator or an authorized representative who is experienced in the evaluation of ECGs and assessed for clinical significance.

The ECG individual data (including clinical significance that will be reported as AE) will be entered into the electronic data capture (EDC).

8.2.7 CLINICAL SAFETY LABORATORY ASSESSMENTS

See [Appendix 10](#) for the list of clinical laboratory tests to be performed and the SoA (see Section 1.3) for the timing and frequency of the tests.

A central laboratory will be used to perform all laboratory tests except urine pregnancy dipstick which will be assessed by the study center staff. However, local laboratory tests will be allowed in the event that the central laboratory results will not be available immediately and the Investigator needs to make an immediate decision for any safety concerns based on laboratory results. If a local sample is required, it is important that the sample for central analysis is obtained at the same time.

The Investigator must review the laboratory report, document this review, and record any clinically relevant changes occurring during the study in the AE section of the eCRF. The laboratory reports must be filed with the source documents. Clinically significant abnormal laboratory findings are those that are not associated with the underlying disease, unless judged by the Investigator to be more severe than expected for the subject's condition.

For screening laboratory assessments, if any laboratory results are outside of the upper or lower limits listed in [Section 5.1](#), final determination of eligibility will be at the Investigator's discretion following consultation with the Medical Monitor and Sponsor.

All laboratory tests with values considered clinically significantly abnormal during the study and including the subject's last study visit (EOS) should be repeated until the values return to normal or Baseline or are no longer considered clinically significant or judged medically stabilized by the Investigator or Medical Monitor.

If such values do not return to normal/Baseline within a period of time judged reasonable by the Investigator, the etiology should be identified, and the Sponsor notified.

All protocol-required laboratory assessments, as defined in Appendix 10, must be conducted in accordance with the Laboratory Manual and the SoA.

If laboratory values from nonprotocol specified laboratory assessments performed at the institution's local laboratory require a change in subject management or are considered clinically significant by the Investigator (eg, SAE or AE), then the results must be recorded in the eCRF.

8.2.8 TELEPHONE CONTACT

At Days 3, 15, 43 and 71, subjects will be contacted by phone to assess for safety. Study staff will review for any new AEs or changes in concomitant medications. Any new/changed AEs and concomitant medications will be recorded on the eCRF.

DocuSign Envelope ID: E4BE9C16-DB1E-4354-B874-2109B7254DAA

Efficacy and Safety of ANB019 in Subjects with Ichthyosis
Protocol ANB019-206

Version 1.0
30 October 2020

8.3 OTHER ASSESSMENTS

8.3.1 PHOTOGRAPHY

Photography (of total body and representative lesion[s] of skin scaling and erythema) will be performed at selected study centers only at the time points mentioned in the SoA (see [Section 1.3](#)) for documentation purposes only.

Additional information on photography will be described in the manual provided to sites.

8.3.2 PHARMACOKINETICS

Whole blood will be obtained for the determination of ANB019 concentration in human serum. Samples will be collected according to the SoA (see Section 1.3) and [Table 4](#). Whole blood will be obtained from each subject for PK assessments during the study. Each serum sample will be divided into 2 aliquots (1 each for primary and a back-up). Samples collected for analyses of ANB019 serum concentration may also be used to correlate exposure to safety or efficacy as well as supportive analysis for dose justification.

The actual date and time (24-hour clock) of the blood sample collection will be recorded in the subject's eCRF. The details of blood sample collection, sample tube labeling, sample preparation, storage, and shipping procedures will be described in a separate manual.

The measurement of the concentrations of ANB019 will be performed using a validated assay method under the supervision of the Sponsor. The analytical methods used to measure concentrations of ANB019 will be described in a separate bioanalytical report.

Only samples within the stability window of the assay will be analyzed.

While PK samples must be collected from subjects assigned to the placebo arm to maintain the blinding of treatment assignment, PK assay results for these subjects are not needed for the safe conduct or proper interpretation of this study. These samples may not be analyzed unless needed to investigate if a dosing error has occurred. Personnel at the bioanalytical laboratory performing PK assays will be unblinded, the clinical study team members, and study center staff (with the exception of the unblinded Pharmacist) will remain blinded to treatment for the duration of the study. Data may be de-identified for quality review. Additional details on de-identification or unblinding of the PK data, if applicable, will be described in a separate plan.

Drug concentration information that may unblind the study will not be reported to study centers or blinded personnel until the study has been unblinded.

DocuSign Envelope ID: E4BE9C16-DB1E-4354-B874-2109B7254DAA

Efficacy and Safety of ANB019 in Subjects with Ichthyosis
Protocol ANB019-206

Version 1.0
30 October 2020

Table 4: Pharmacokinetic Sample Collection and Time Points

Study Visit	Pharmacokinetic Sample Time Point (Serum)	Adults (≥ 18 years)	Adolescents (≥ 12 to < 18 years) ^a
Day 1	Predose	X	X
	2 hrs (± 10 min) postdose	X	X
Day 8	Anytime	X	
Day 29	Predose	X	X
Day 57	Predose	X	X
Day 85	Predose	X	
Day 113	Predose	X	X
Day 141	Predose	X	
Day 169	Predose	X	
Day 197	Predose	X	
Day 225	Anytime	X	X
Day 253	Anytime	X	
Day 281	Anytime	X	X

Abbreviations: hrs, hours; min, minutes.

^a Adolescent subjects who reach 18 years of age during the study and are reconsented as adults will follow the adult schedule of assessments.

8.3.3 IMMUNOGENICITY ASSESSMENTS

Anti-drug antibodies (ADA) to ANB019 will be evaluated in serum samples collected from all subjects according to the SoA (see [Section 1.3](#)) and [Table 5](#). Additionally, serum samples should also be collected at the final visit from subjects who discontinued study treatment or were withdrawn from the study. These samples will be tested by the Sponsor or Sponsor's designee. Each serum sample will be divided into 2 aliquots (1 each for primary and a back-up).

The detection and characterization of antibodies to ANB019 will be performed using a validated assay method by or under the supervision of the Sponsor.

Serum samples will be tested in a multi-tiered approach. A validated screening assay for antibodies binding to ANB019 will be initially used to assess serum samples. Samples that are determined putative positive in the screening assay will then be subjected to a confirmatory assay to demonstrate that antibodies are specific to ANB019. Samples that are identified as positive in the confirmatory assay will be further characterized in a validated titer assay and the titer of confirmed positive samples will be reported. Other analyses may be performed to verify the stability of antibodies to study treatment and/or to further characterize the immunogenicity of study treatment.

Samples that are confirmed positive for antibodies binding to ANB019 may be further characterized for their ability to neutralize the activity of the study treatment using a validated neutralizing antibody assay method and the presence and/or titer of ADA may be correlated to safety and PK data.

DocuSign Envelope ID: E4BE9C16-DB1E-4354-B874-2109B7254DAA

Efficacy and Safety of ANB019 in Subjects with Ichthyosis
Protocol ANB019-206

Version 1.0
30 October 2020

Table 5: Anti-Drug Antibodies Sample Collection and Time Points

Study Visit	Anti-Drug Antibodies Sample Time Point (Serum)	Adults (≥ 18 years)	Adolescents (≥ 12 to < 18 years) ^a
Day 1	Predose	X	X
Day 29	Predose	X	X
Day 57	Predose	X	X
Day 85	Predose	X	
Day 113	Predose	X	X
Day 141	Predose	X	
Day 225	Anytime	X	X
Day 281	Anytime	X	X

^a Adolescent subjects who reach 18 years of age during the study and are reconsented as adults will follow the adult schedule of assessments.

8.3.4 IMMUNOGLOBULIN E LEVELS EVALUATION

Whole blood will be obtained from subjects with Netherton Syndrome for the evaluation of IgE levels. Samples will be collected according to the SoA (see [Section 1.3](#)). The quantification of IgE will be performed by the Sponsor or Sponsor's designee using a validated method. Samples collected for IgE levels evaluation may also be used to correlate with safety or efficacy results.

The actual date and time of the sample collection will be recorded in the subject's eCRF. The details of blood sample collection, sample tube labeling, sample preparation, storage, and shipping procedures will be described in a separate manual.

8.3.5 BIOMARKERS ANALYSIS

8.3.5.1 TAPE STRIPPING

Tape strips samples will be collected according to the SoA (see Section 1.3) to measure cutaneous biomarkers including but not limited to IL-36R, Th-17 cytokines such as IL-17A, and markers of neutrophils and dendritic cells infiltration.

The actual date and time of the sample collection will be recorded in the subject's eCRF. The details of tape strips collection, sample tube labeling, sample preparation, storage, and shipping procedures will be described in a separate Laboratory Manual.

The measurement of tape strips biomarkers may be performed by an additional third party (eg, a university Investigator) designated by the Sponsor.

8.3.5.2 OPTIONAL SKIN BIOPSY

Optional skin biopsy samples will be collected according to the SoA (see Section 1.3) to measure skin biopsy biomarkers including but not limited to IL-36R, Th-17 cytokines such as IL-17A, and markers of neutrophils and dendritic cells infiltration.

The actual date and time of the sample collection will be recorded in the subject's eCRF. The details of skin biopsy collection, sample tube labeling, sample preparation, storage, and shipping procedures will be described in a separate Laboratory Manual.

DocuSign Envelope ID: E4BE9C16-DB1E-4354-B874-2109B7254DAA

Efficacy and Safety of ANB019 in Subjects with Ichthyosis
Protocol ANB019-206

Version 1.0
30 October 2020

The measurement of skin biopsy biomarkers may be performed by an additional third party (eg, a university Investigator) designated by the Sponsor.

DocuSign Envelope ID: E4BE9C16-DB1E-4354-B874-2109B7254DAA

Efficacy and Safety of ANB019 in Subjects with Ichthyosis
Protocol ANB019-206

Version 1.0
30 October 2020

9 STATISTICAL CONSIDERATIONS

9.1 STATISTICAL HYPOTHESES

The primary analysis for this study is to compare the mean IASI score for ANB019 with placebo during the double-blind treatment period, at a two-sided alpha = 0.05 level. Any testing being performed for secondary or exploratory endpoints will be considered exploratory in nature based on a 2-sided alpha = 0.05

$H_0: \mu_{ANB019} - \mu_{Placebo} = 0$ vs. $H_A: \mu_{ANB019} - \mu_{Placebo} \neq 0$

9.2 SAMPLE SIZE DETERMINATION

The primary efficacy endpoint is the change from Baseline of the IASI score at Week 16. The null hypothesis (H_0) to be tested is that the mean change in IASI score from Baseline is the same for ANB019 and placebo. Assuming a 0.5 correlation between Baseline IASI and Week 16 IASI, a common standard deviation (SD) of 9, and a 11% dropout rate, an enrollment of 16 subjects (leaving 14 after dropout) in the ANB019 treatment arm and 8 subjects (leaving 7 after dropout) will have at least 80% power to detect the overall treatment effect for a two sample t-test using a 2-sided significance level of 0.05, where the difference in the mean reduction from Baseline between one of the ANB019 groups and the placebo group is assumed to be 12.3 points. A placebo response is anticipated for this study sample and assumed to be an approximate 10% improvement from the Baseline in the IASI score. If the mean Baseline IASI score is 30, this represents a 3-point reduction in the score for the placebo group. The ANB019 group is assumed to achieve a mean reduction of 15.3 points, assuming the same Baseline mean score of 30.

9.3 POPULATIONS FOR ANALYSES

The analysis sets are defined in Table 6.

Table 6: Analysis Sets

Analysis Set	Description
ITT Analysis Set	The ITT analysis set will include all randomized subjects. In this analysis set, treatment will be assigned based upon the treatment arm to which subjects were randomized regardless of which treatment they receive.
Safety Analysis Set	The safety analysis set will include all randomized subjects who receive 1 dose of ANB019 or placebo. The safety analysis set will be used for all safety analyses. Subjects will be analyzed as treated.
Per Protocol Analysis Set	The per protocol analysis set will include all subjects in the ITT analysis set who do not have major protocol violations that would affect the evaluation of the primary efficacy endpoint.
PK Analysis Set	The PK analysis set will include all ANB019 treated subjects in the safety analysis set who have at least 1 quantifiable postdose PK sample available and who do not have events or protocol deviations or events with the potential to affect PK concentrations. The PK analysis set will be used for all PK analyses.

Abbreviations: ITT, intent-to-treat; PK, pharmacokinetic.

DocuSign Envelope ID: E4BE9C16-DB1E-4354-B874-2109B7254DAA

Efficacy and Safety of ANB019 in Subjects with Ichthyosis
Protocol ANB019-206

Version 1.0
30 October 2020

9.4 STATISTICAL ANALYSES

9.4.1 GENERAL APPROACH

The statistical analysis will be performed using statistical analysis system (SAS[®]) Version 9.4 or higher. All details regarding the statistical analysis and the preparation of tables, listings, and figures will be described in the Statistical Analysis Plan (SAP) and approved by the Sponsor before database lock and any analysis is undertaken.

The default summary statistics for continuous variables include number of contributing observations, mean, SD, median, minimum, and maximum. For PK parameters, coefficient of variation (CV) and geometric mean will also be presented, as appropriate.

For categorical variables, the number and percentage (percentage of subjects in each category relative to the total number of subjects in the relevant analysis set or relative to the total number of subjects in the relevant analysis set with assessments available [where appropriate]) in each category will be the default summary presentation.

Unless otherwise specified, "Baseline" is defined as the last observed value of the parameter of interest prior to the first intake of study treatment (this includes unscheduled visits). For numerical variables, change from Baseline will be calculated as the difference between the value of interest and the corresponding Baseline value.

Unless otherwise specified, all formal statistical tests will be 2-sided at the 5% significance level. Point estimates of treatment differences will be accompanied with 2-sided 95% confidence intervals (CIs), where applicable.

In the case of normality assumption violations, appropriate nonparametric methods may be used for analysis.

All data will be presented in by-subject listings.

9.4.2 SUBJECT DISPOSITION

A tabular presentation of the subject disposition will be provided. It will include the number of subjects screened, randomized, treated, completed as well as the number of dropouts with reasons for discontinuation, and major protocol deviations or violations.

A listing will be presented to describe dates of screening, assigned treatment, screen failed with reason, completion or early withdrawal, and the reason for early discontinuation, if applicable, for each subject. A list of protocol deviations/violations will be identified and discussed with the Investigator/Sponsor in dry run to categorize as major or minor with decisions of exclusion from analysis sets prior to unblinding.

During the COVID-19 pandemic, protocol deviations related to COVID-19 will be documented and information on how they will be handled in the analyses will be detailed in the SAP.

9.4.3 BASELINE DESCRIPTIVE STATISTICS

Subject characteristics obtained at Baseline will be summarized for all subjects taking ANB019 or placebo.

Summaries will include descriptive statistics for continuous variables (sample size [n], mean, SD, median, minimum, and maximum) and for categorical variables (n, frequency, and percentage).

Medical history will be coded using the Medical Dictionary for Regulatory Activities (MedDRA) latest version and listed for all subjects.

DocuSign Envelope ID: E4BE9C16-DB1E-4354-B874-2109B7254DAA

Efficacy and Safety of ANB019 in Subjects with Ichthyosis
Protocol ANB019-206

Version 1.0
30 October 2020

9.4.4 CONCOMITANT MEDICATION

All medications will be coded using the World Health Organization (WHO) Drug Dictionary and Anatomical Therapeutic Chemical (ATC) system. Each medication will be classified as prior medication if it is stopped prior to the first dose of study treatment, or as concomitant medication if it is ongoing at the time of the first dose or is started after the first dose of study treatment. Prior, concomitant, and rescue medications will be summarized descriptively with a by-subject listing.

9.4.5 ANALYSIS OF THE PRIMARY EFFICACY ENDPOINT

The primary efficacy endpoint is the change from Baseline in IASI total score at Week 16.

A general linear mixed model repeated measures (MMRM) analysis will be used to estimate the least-squares means (LSM) and associated standard errors for the change from Baseline in IASI total score to Week 16. The model will include change from Baseline in IASI total score at Week 16 as the dependent variable, fixed effects for treatment arm, categorical time point, and the treatment by time point interaction, and the Baseline IASI total score as a covariate. An appropriate covariance structure will be described in the SAP prior to database lock. Should the initial model not converge, alternate covariance structures or inclusion of fewer postBaseline visits (eg, Week 8 and Week 16 only) will be considered. Full details will be described in the SAP. The difference between LSMs (ANB019 – placebo) at Week 16 will be presented along with the associated 95% CI and p-value.

Possible effect of any other covariates as well as investigation of variables through sub-group analysis may also be investigated. Details of such analyses will be described in the SAP. Details of specific alternative statistical methods will be documented in the SAP.

In addition, descriptive statistics (n, mean, SD, median, minimum, and maximum) will be presented by visit.

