4 STUDY DESIGN

4.1 OVERALL DESIGN

This is a Phase 2, multicenter, randomized, double-blind, placebo-controlled study to evaluate the efficacy, safety, and tolerability of ANB019 compared with placebo in adolescent and adult subjects with ichthyosis. This study will also characterize the PK profile of ANB019 and explore the immune response to ANB019 in subjects with ichthyosis.

Approximately 24 male and female adolescent and adult subjects with clinically confirmed diagnosis of ichthyosis (as described in [Section 5.1](#)) will be enrolled in this study. To be eligible for the study, the subjects will need to have a diagnosis of their ichthyosis subtype confirmed by genetic testing. In addition, the subjects will have the following characteristics at Day 1: IASI total score of at least 18, erythema score of at least 2 (moderate severity) in at least 1 body region and scaling score of at least 2 (moderate severity) in at least 1 body region as evaluated by IASI, and BSA involved with ichthyosis of at least 50%. Randomization will be stratified based on erythema severity at Baseline (highest severity [moderate {2} vs severe/very severe {3, 4}] as evaluated by IASI-E).

Written informed consent will be obtained from each subject prior to initiating any study related procedures. Subjects will also provide consent for skin biopsy collection if they wish to participate in this test.

The expected study duration per subject is approximately 44 weeks. The study will include a screening period of up to 30 days, followed by a 16-week placebo-controlled period, a 16-week open-label extension period, and an 8-week safety follow-up period.

Of note, all subjects will receive ANB019 during the open-label extension period starting on Day 113 (Week 16) visit until Day 197 (Week 28) visit. The placebo-controlled period ends on Day 113 (Week 16) visit, before study treatment administration. Therefore, the open-label extension period starts when the study treatment is administered on Day 113 (Week 16) visit.

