6.3 MEASURES TO MINIMIZE BIAS: RANDOMIZATION AND BLINDING

This study includes a randomized, double-blind, placebo-controlled period followed by an open-label period. The blind will be maintained throughout the study with limited and controlled access to the randomization code.

All subjects will be assigned a unique 'subject identification number' at the time of screening. On Day 1, after verification that all inclusion and no exclusion criteria have been met, the subjects will be randomized in a 2:1 ratio to receive ANB019 or placebo. As subjects become eligible, they will be assigned unique randomization numbers, which will be used to assign the allocated treatment based on a randomization schedule. Randomization will be stratified based on erythema severity at Baseline (highest severity [moderate {2} vs severe/very severe {3, 4}] as evaluated by IASI-E).

The Sponsor, Investigator, and subjects will be blinded to treatment assignment of ANB019 or placebo. An unblinded Pharmacist will be responsible for study treatment dispensing.

Once the subject has provided an informed consent and meets all inclusion and no exclusion criteria, the study center will request the treatment assignment using a central Interactive Web Response System (IWRS).

The process for breaking the blind will be handled through the IWRS. Unblinding is undertaken by a predetermined process to ensure that participating subject and study team are not unblinded unnecessarily and the study results are not compromised. Unblinding of treatment assignment during the study should occur only if it is necessary to know what treatment the subject received during the placebo-controlled period. Unblinding should occur if the Investigator deems identification of the study treatment is necessary for the purpose of providing urgent subject care, and knowledge of the subject's treatment assignment (ANB019 or placebo) will alter subsequent care (emergency unblinding).

In the event that emergency unblinding is necessary, the Investigator must ensure that the unblinding of the treatment code is performed in a discrete manner and the treatment is disclosed only to those persons involved with the direct medical care of the subject. The Investigator must provide the reason for unblinding to the Sponsor's Medical Monitor according to the Sponsor instructions following emergency unblinding.

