Appendix 8: Ichthyosis Area Severity Index

The IASI (Paller 2017, Malik 2019, Czarnowicki 2018) incorporates extent through the techniques used for assessment in the Eczema Area and Severity Index (EASI) and Psoriasis Area and Severity Index (PASI) scores for atopic dermatitis and psoriasis, respectively.

The steps for the IASI are as follows:

- Determine mean **INTENSITY** of erythema and scaling separately within four body regions (A1 = head and neck; A2 = upper limbs; A3 = trunk; A4 = lower limbs) as seen on the day of the examination. The intensity of redness/erythema and scaling of the ichthyosis is assessed using a 5-point scale (can be integer or with .5):

0	None
1	Mild
2	Moderate
3	Severe
4	Very Severe

- Determine what percentage of **AREA** within a body region is affected by ichthyosis (B1 = percentage within head and neck; B2 = percentage within upper limbs; B3 = percentage within trunk; B4 = percentage within lower limbs). The area affected by ichthyosis within a given body region is estimated as a percentage of the total area of that body region and is assigned a numerical value according to the degree of ichthyosis involvement as follows:

% involvement	0	1-9%	10 - 29%	30 - 49%	50 - 69%	70 - 89%	90 - 100%
Region score	0	1	2	3	4	5	6

- Determine **TOTAL EXTENT** by using a multiplier that takes into account the percentage of the total body surface area represented by each body region (C1 = 0.1 for head and neck; C2 = 0.2 for upper limbs; C3 = 0.3 for trunk; C4 = 0.4 for lower limbs).

The **IASI-E** is obtained by using the formula below:

$$\begin{aligned} \text{IASI-E} = & A1 \text{ erythema} \times B1 \times C1 + A2 \text{ erythema} \times B2 \times C2 + A3 \text{ erythema} \times B3 \times C3 \\ & + A4 \text{ erythema} \times B4 \times C4 \end{aligned}$$

The **IASI-S** is obtained by using the formula below:

$$\text{IASI-S} = A1 \text{ scaling} \times B1 \times C1 + A2 \text{ scaling} \times B2 \times C2 + A3 \text{ scaling} \times B3 \times C3 + A4 \text{ scaling} \times B4 \times C4$$

The **IASI TOTAL SCORE** (max potential 48) = IASI-E (max potential = 24) + IASI-S (max potential = 24).

DocuSign Envelope ID: E4BE9C16-DB1E-4354-B874-2109B7254DAA

Efficacy and Safety of ANB019 in Subjects with Ichthyosis
Protocol ANB019-206

Version 1.0
30 October 2020

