3.2 Randomization

On Day 1, after verification that all inclusion and no exclusion criteria have been met, the subjects will be randomized in a 2:1 ratio to receive imsidolimab or placebo. Randomization will be stratified based on erythema highest severity at baseline as evaluated by IASI-E [moderate (2) vs severe/very severe (3, 4)]. Subjects who receive the wrong treatment will be analyzed according to the treatment they were supposed to be randomized to in the efficacy analyses. In the safety analyses, subjects will be analyzed according to the treatment they actually received.

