7.3 Efficacy Analyses

Due to study termination, no efficacy analysis will be performed. All efficacy data will be listed in data listings.

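### Should the primary MMRM include the erythema stratum used in the randomisation?

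*Protocol*

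**What the plan says.** Protocol 4.1 sets one stratification factor: "Randomization will be stratified based on erythema severity at Baseline (highest severity [moderate {2} vs severe/very severe {3, 4}] as evaluated by IASI-E". Protocol 4.3 and 6.3 and SAP 3.2 give the same factor and the same two levels.

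Protocol 9.4.5 models change from Baseline in IASI total with "fixed effects for treatment arm, categorical time point, and the treatment by time point interaction, and the Baseline IASI total score as a covariate". The stratum is not in the list. The section then says: "Possible effect of any other covariates as well as investigation of variables through sub-group analysis may also be investigated". It names no further covariate and leaves the details to the SAP.

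The SAP contains no efficacy model. Section 1 reports termination for low enrolment, Section 8 says the analyses are much reduced, and Section 7.3 states: "Due to study termination, no efficacy analysis will be performed". The stratum survives only in listings (SAP 7.1).

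On scoring, Protocol Appendix 8 says: "The intensity of redness/erythema and scaling of the ichthyosis is assessed using a 5-point scale (can be integer or with .5".

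**The concern.** Stratified allocation makes the arms more alike on erythema than chance alone would. A model without the stratum does not know this. If the stratum predicts outcome, its variance stays in the residual although the design has already removed it from the treatment comparison. The reported standard error is then too large, the confidence interval too wide, and the test rejects less often than 5% under the null. With 21 evaluable subjects, lost sensitivity is unwelcome, and one extra main effect looks almost free.

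There is also a small gap in wording. Half-point scores are allowed and entry requires erythema of at least 2 in one region, so a subject whose highest score is 2.5 is eligible but belongs to neither listed level.

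**Working it through.** **Inputs.** Protocol 9.2 sizes the trial "Assuming a 0.5 correlation between Baseline IASI and Week 16 IASI, a common standard deviation (SD) of 9, and a 11% dropout rate", with a difference of 12.3 points, two-sided 5% significance, 16 + 8 enrolled and 14 + 7 evaluable. The documents do not give the share of subjects in the severe stratum, the block size, or the stratum's effect on outcome given Baseline IASI. These are assumed below.

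**1. The plan's own power.** SD of change = 9 × √(2 × (1 − 0.5)) = 9.0. SE = 9 × √(1/14 + 1/7) = 4.17. Noncentrality = 12.3 / 4.17 = 2.95 on 19 df, giving power of 79.97%. Exactly 80% needs 12.305 points, so the stated figure reproduces. Dropout also agrees: 16 × 0.89 = 14.2 and 8 × 0.89 = 7.1.

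**2. Cost of the term if erythema is not prognostic.** Adjusting for Baseline IASI gives a residual SD of 9 × √(1 − 0.5²) = 7.79 (variance 60.75). Without the stratum there are 18 df, critical t 2.101 and power 89.7%. With it there are 17 df, critical t 2.110 and power 89.5%. The cost is 0.2 points. This holds for a main effect only; a stratum-by-visit term would cost more.

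**3. What an assumed shift means.** With share p in the severe stratum and a shift of b points given Baseline IASI, the stratum explains p(1 − p)b² / 60.75 of the residual variance. At p = 0.5 this is 4 / 60.75 = 7% for 4 points and 16 / 60.75 = 26% for 8 points.

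**4. Simulation at the protocol's SD.** A Week 16 ANCOVA stands in for the MMRM contrast. There are 24 randomised 2:1 in blocks of 3 within stratum, 14 versus 7 analysed, residual variance held at 60.75 including the stratum's share, and 10,000 trials per cell. Monte Carlo SE is about 0.2 points for type I error and 0.3 for power. Each cell shows the result without, then with, the stratum.

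| Severe share | Shift | Type I error, % | Power at 12.3, % | Mean 95% CI width |
|---|---|---|---|---|
| 50% | 0 | 4.5, 4.7 | 88, 87 | 15.4, 15.6 |
| 50% | 4 | 3.8, 4.4 | 89, 90 | 15.4, 15.0 |
| 50% | 8 | 2.6, 4.7 | 90, 95 | 15.5, 13.3 |
| 80% | 0 | 5.0, 4.8 | 88, 87 | – |
| 80% | 4 | 4.8, 5.3 | 88, 88 | – |
| 80% | 8 | 3.4, 5.0 | 90, 93 | – |
| 50%, erythema correlated 0.5 with Baseline IASI | 4 | 4.3, 4.7 | 88, 89 | – |
| 50%, erythema correlated 0.5 with Baseline IASI | 8 | 3.4, 5.2 | 89, 94 | – |

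A repeat run at shifts of 0, 4 and 8 gave type I error of 5.0, 4.2 and 2.8% without the stratum, and 5.4, 4.8 and 4.6% with it. At zero shift both models are correct, so departures from 5% there are simulation noise.

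**5. Bias and real precision.** Mean bias of the treatment estimate is at most 0.08 points in any cell. In the repeat run, the true SD of the estimate was 3.63 without and 3.62 with the stratum at 4 points, and 3.35 versus 3.23 at 8 points. Most of the narrower interval therefore comes from a reported SE that matches the design: in the first run at 8 points, the model without the stratum reported 3.69 against a true 3.30, about 12% too large.

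**6. Does the model get used?** Protocol 9.4.5 describes it, but SAP 7.3 withdraws it. No output in the SAP's list of tables and listings depends on it.

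**The case for a change.** The best case for a change has three parts.

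*Analysing as randomised is sound practice, and Baseline IASI total does not stand in for the stratum.* By Appendix 8, with an area score of 6 in every region, erythema 2 and scaling 3 give 12 + 18 = 30, while erythema 3 and scaling 2 give 18 + 12 = 30. The covariate is the same but the strata differ. This stands, although IASI-E can supply 24 of the 48 points, so erythema is partly adjusted for already.

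*The power loss could be larger.* If the stratum's variance is added to the residual variance instead of being contained in it, a 9-point effect at a 50% severe share gives type I error of 2.9% without and 4.9% with the stratum, power of 80.1% and 87.4%, and a reported SE of 4.22 and 3.67. At 13.5 points, power without the stratum falls to 70.1%, against 87.7% with it. These cases leave the planning assumptions: they add up to 9² × 0.25 = 20.25 or 13.5² × 0.25 = 45.56 to 60.75, taking the residual SD from 7.79 to about 9.0 or 10.3. Even at 9 points, the true SD of the estimate is 3.79 versus 3.70.

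*The SAP did not put the stratum back.* That is true, but it has little weight. The protocol deferred covariates to the SAP, and the SAP that followed termination has no efficacy model in which the stratum could appear. Its silence is not a decision to leave the stratum out.

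The 2.5-score gap is real on the text. The specification of the randomisation system is not among the documents, so how such a score was handled is unknown. The score is a baseline value, and randomisation remains valid whichever stratum received it.

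**Conclusion.** No change is needed, because there is nothing to gain in this trial. The omission is real, but it errs on the conservative side: there is no bias, no inflation of the type I error, and power stays above the planned 80% in every case that keeps the protocol's SD. The benefit of adding the stratum depends on a prognostic effect that the documents do not establish. It is 0 to 1 power points at a 4-point shift, 3 to 5 points at 8 points, and a loss of up to 1 point if there is no effect. An 8-point shift is large, close to the full SD of 9 and about two-thirds of the planned difference (8 / 12.3 = 0.65). With all efficacy analysis cancelled, none of this reaches a reported estimate, interval or decision.

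The conclusion rests on SAP 7.3 remaining in force and on an ANCOVA representing the Week 16 MMRM contrast. If the model were reused in another study, the stratum would belong in it as a main effect, and the level for a highest score of 2.5 would need to be defined.
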